4.7.4. Vital Signs and Physical Examination

The observed values and changes from baseline in weight and vital signs, including blood pressure, pulse rate, oral body temperature and respiration rate, will be summarized by scheduled visit. The frequency and percentage of patients with an abnormal change from baseline in pulse rate or blood pressure measures will also be presented.

Vital sign measurements will be presented for each patient in a data listing.

All abnormal physical examination findings will be presented in a by-patient data listing.

4.7.5. Ophthalmology Examinations

Ophthalmology examinations include Visual Acuity, Slit Lamp Biomicroscopy, and Visual Field assessments.

Visual Acuity and Visual Field Exam Results: The actual value and change from baseline results will be summarized by scheduled visit.

Biomicroscopy (Slit Lamp) Exam Results: For the baseline results, the number and percentage of patients falling into each category of the examination status (normal, abnormal/not clinically significant, abnormal/clinically significant) will be summarized for each eye structure. For post-baseline results, the number and percentage of patients falling into each category of the examination status (new findings/worsening of finding, no change, improvement of finding) will be summarized for each eye structure.

Data for each of these assessments will be provided in a data listing.

4.7.6. Premedications

All patients will receive premedication prior to the dose of patisiran in order to reduce the potential of an IRR. The original premedication regimen as outlined below was used at the start of the study. A subset of patients experienced AEs suspected to be related to steroids (e.g., flushing) and were transitioned to a reduced premedication regimen, with a reduced dose of corticosteroid to mitigate these events, as sanctioned in the protocol. After observing that the subset of patients tolerated the lower corticosteroid dose with no increase in IRRs, the protocol was amended (Amendment 1.0) to transition the rest of the patients to the reduced premedication regimen (see below).

The following original premedication regimen was used prior to protocol amendment 1.0:

- Dexamethasone 8 mg PO or equivalent administered the evening before dosing and 20 mg PO at least 60 minutes prior to the start of the infusion of patisiran;
- Paracetamol 500 mg PO or equivalent administered the evening before dosing and at least 60 minutes prior to the start of the infusion of patisiran;
- H2 blocker PO (e.g., ranitidine 150 mg or famotidine 20 mg or equivalent other H2 blocker dose) administered the evening before dosing and at least 60 minutes prior to start of the infusion of patisiran; and
- H1 blocker PO, 10 mg cetirizine or equivalent (hydroxyzine 25 mg or fexofenadine could be substituted if patient did not tolerate cetirizine) administered the evening before dosing and at least 60 minutes prior to start of the infusion of patisiran.

The following reduced premedication regimen was instituted for all patients with protocol amendment 1.0:

- Dexamethasone 10 mg IV or equivalent, administered at least 60 minutes prior to the start of the infusion of patisiran;
- Paracetamol 500 mg PO or equivalent at least 60 minutes prior to the start of the infusion of patisiran;
- H2 blocker IV (e.g., ranitidine 50 mg, famotidine 20 mg, or equivalent other H2 blocker dose) at least 60 minutes prior to the start of the infusion of patisiran; and

- H1 blocker IV, diphenhydramine 50 mg (or equivalent other IV H1 blocker available at the study site) at least 60 minutes prior to the start of the infusion of patisiran. Hydroxyzine 25 mg PO or fexofenadine 30 or 60 mg PO or cetirizine 10 mg PO could be substituted for any patient who did not tolerate IV diphenhydramine or other IV H1 blocker.

Premedications will be coded using the WHO Drug Dictionary (March 2015 or later). Results will be tabulated by anatomic therapeutic class (ATC) and PT. Premedication data will be listed.

4.7.7. Concomitant Medications

Concomitant medications will be defined as those medications that were initiated after first patisiran administration in this extension study or those that were ongoing at the time of the first patisiran administration in this study. For medications with partial start or stop dates: the first day/month will be imputed for start date, and the last day/month will be imputed for stop date. For medications with a completely missing start date, the medications will be considered as started prior to the first dose of study drug; medications will be classified as prior, concomitant or both depending on the medication stop dates. For medications with a completely missing stop date, the earlier of the data cut-off date or the end of study date will be imputed.

Concomitant medications will be coded using the WHO Drug Dictionary (March 2015 or later). Results will be tabulated by ATC and PT; patients will only count once for each ATC or PT in the event that they have multiple medications with the same ATC or PT. Medications taken as protocol-specified premedications will be summarized separately.

Concomitant medications will be included in a by-patient data listing.

4.7.8. Suicide Questionnaire

The numbers and percentages of patients experiencing the suicidal ideation, suicidal behavior, or self-injurious behavior composite outcomes (and individual components thereof) during the treatment period will be summarized. A shift table will be employed to summarize the baseline C-SSRS category versus the worst post-baseline C-SSRS category; the categories are defined as 1) no suicidal ideation or behavior, 2) suicidal ideation, and 3) suicidal behavior. Subjects experiencing both suicidal ideation and suicidal behavior are included in the suicidal behavior category.

Data from the C-SSRS questionnaire will be provided in a data listing.

4.8. Anti-Drug Antibody

Anti-drug antibody data will be presented in a data listing. Patients with positive ADA results will be presented in a separate listing.

5. CHANGES TO PLANNED ANALYSES

In the protocol, the first day of drug administration in this study was designated as Day 0. In the SAP and table/listing/figure outputs, the first dose day will be defined as Day 1, following CDISC convention. Each calculated study day after dosing is 1 day plus the reported study day following the protocol defined Schedule of Assessments.

In addition to IENFD and SGNFD, skin punch biopsies will also be assessed for dermal amyloid content, which has been added as an efficacy parameter.

7. QUESTIONNAIRE/SCORING APPENDICES

In questionnaires, if multiple responses are provided to a single-response question, the question is deemed as missing.

7.1. Modified Neuropathy Impairment Score + 7 (mNIS+7) and Neuropathy Impairment Score + 7 (NIS+7)

Note: the mNIS+7 and NIS+7 measurements are conducted in duplicate per time point. The average of 2 complete duplicate values will be reported, except in cases of missing or partially missing data as described below.

Assessment Tool	Total Points	Components (maximum points)
mNIS+7	304	
 • NIS-W: Weakness (192) • NIS-R: Reflexes (20) • Quantitative sensory testing by body surface area including touch pressure (TP) and heat as pain (HP): QST-BSA_{TP+HP5} (80) • $\sum 5$ nerve conduction studies (10) 
 • Ulnar compound muscle action potential (ulnar CMAP) • Ulnar sensory nerve action potential (ulnar SNAP) • Sural sensory nerve action potential (sural SNAP) • Tibial compound muscle action potential (tibial CMAP) • Peroneal compound muscle action potential (peroneal CMAP) • Postural blood pressure (BP) (2)
NIS+7	270	
 • NIS-W: Weakness (192) • NIS-R: Reflexes (20) • NIS-S: Sensation (32) • $\sum 7$ Nerve tests 
 • 5 Nerve conduction studies $\sum 5$ (18.6) 
 • Peroneal compound muscle action potential (peroneal CMAP) • Peroneal motor nerve conduction velocity (peroneal MNCV) • Peroneal motor nerve distal latency (peroneal MNDL) • Tibial motor DL • Sural sensory nerve action potential (sural SNAP) • Vibration detection threshold (VDT) (3.72) • Heart rate response to deep breathing (HRdb) (3.72)

7.1.1.1. Modified Neuropathy Impairment Score + 7 (mNIS+7)

There are 5 components within mNIS+7 total score including NIS-W, NIS-R, QST, $\Sigma 5$ NC, and postural BP, as described in detail below.

1. NIS-W is the sum of the cranial nerve components (3rd nerve, 6th nerve, facial weakness, palate weakness, tongue weakness) and muscle weakness components (respiratory, neck flexion, shoulder abduction, elbow flexion, brachioradialis, elbow extension, wrist flexion, wrist extension, finger flexion, finger spread, thumb abduction, hip flexion, hip extension, knee flexion, knee extension, ankle dorsiflexors, ankle plantar flexors, toe extensors, toe flexors). Assessments are performed separately for the right- and left-hand side of the body. Scoring for each component is 0 (normal), 1 (25% weak), 2 (50% weak), 3 (75% weak), 3.25 (move against gravity), 3.5 (movement, gravity eliminated), 3.75 (muscle flicker, no movement), and 4 (paralysis). The maximum total score for NIS-W is 192.
2. NIS-R is the sum of the reflex components (biceps brachii, triceps brachii, brachioradialis, quadriceps femoris, and triceps surae). Assessments are performed separately for the right and left foot. Scoring for each component is 0 (normal), 1 (decreased) and 2 (absent). Adjustments are made for the age of the patient (e.g., absent reflexes in a patient older than 60 is assessed as 0, or normal). The maximum total score for NIS-R is 20.
3. QST measures HP and TP from among 10 distributed anatomical sites on one side of the body. Scoring is based on point abnormality (<95th = 0 point, $\geq 95^{\text{th}} - < 99^{\text{th}}$ = 1 point and $\geq 99^{\text{th}}$ = 2 points). The test score is 2 times the total scores for QST of HP by body surface area (QST-BSA_{HP}) and QST of TP by body surface area (QST-BSA_{TP}). The maximum total score for QST is 80. Missing values for QST-BSA_{HP} and QST-BSA_{TP} will be imputed separately (see below), but only the total score will be summarized.
4. $\Sigma 5$ nerve conductions include ulnar CMAP, ulnar SNAP, sural SNAP, tibial CMAP, and peroneal CMAP. Their measured values were transformed to normal deviates from percentile values correcting for applicable variables of age, gender, height or weight as based on earlier studies of a large healthy patient reference cohort. Additionally, these percentile values were expressed as points from obtained percentile values (i.e., $> 5^{\text{th}}$ = 0 points; $\leq 5^{\text{th}} - > 1^{\text{st}}$ = 1 point and $\leq 1^{\text{st}}$ = 2 points (and similarly when abnormality is in the upper tail of the normal distribution). The total score is calculated as the mean point scores of the non-missing 5 nerve tests and multiply this value by 5. The maximum total score for $\Sigma 5$ NC is 10.
5. Postural BP test measures autonomic function to address risk of orthostasis. The points are assigned based on change in PBP (> -20 mmHg = 0 points; $> -30 - \leq -20$ mmHg = 1 point; and ≤ -30 mmHg = 2 points).

If at least 1 value at a time point and (replicate) assessment is missing then do the following:

- Missing items within the $\Sigma 5$ NCs component (e.g., missing tibial CMAP) are handled in Step 4 above.

- If 1 of the following components or subcomponents of mNIS+7 (NIS-W, NIS-S, QST-BSA_{TP}, QST-BSA_{HP}, the entire $\sum 5$ NCs, or postural BP) is missing from 1 of the assessments at a time point (“replicate A”), then impute via substituting the component from the other assessment at that time point (“replicate B”) → recover 2 complete replicate mNIS+7 measures A and B at that particular time point.
- If both replicates A and B are incomplete at different components, insert replicate A components into replicate B and replicate B components into replicate A as necessary → allow recovery of 2 complete replicate mNIS+7 measures A and B.
- If NIS-W component is missing from both replicates A & B, mNIS+7 score is considered as missing. If 1 of the other mNIS+7 components or subcomponents (NIS-R, the entire $\sum 5$ NCs, QST-BSA_{TP}, QST-BSA_{HP}, or postural BP) is missing from both replicates A and B, impute this component as the average of the component using data from any of the patients who had non-missing data for that component at the time point.
- If 1 entire mNIS+7 replicate is missing, do not impute the missing replicate; just use the singular (other) replicate rather than the average of the 2 in subsequent calculations.
- If no single complete mNIS+7 measure can be found or recovered, mNIS+7 score is considered as missing.

In 006, if the last mNIS+7 assessment in the parent study was done more than 45 days before the first dose in 006, mNIS+7 will be reassessed on Day 1 in 006. It is expected that very few patients will have this Day 1 assessment; therefore, the imputation algorithm for missing components in mNIS+7 will be slightly different from the general algorithm. If NIS-W is missing from both replicates, the mNIS+7 total score will be considered as missing, similar to the general algorithm. If any other component is missing from both replicates, the component score will be imputed by last observation carried forward (LOCF) using the imputed average component score from the last assessment in the parent study.

7.1.2. Neuropathy Impairment Score + 7 (NIS+7)

The components of NIS+7 include the following:

1. NIS-W as described in previous section.
2. NIS-R as described in previous section.
3. NIS-S is the sum of the finger and toe sensation components (TP, pin-prick, vibration, joint position). Assessments are performed separately for the right- and left-hand side of the body. Scoring for the sensory assessment is 0 (normal), 1 (decreased) and 2 (absent). The maximum total score for NIS-S is 32.
4. $\sum 7$ nerve tests normal deviates include the following:
 - $\sum 5$ nerve conductions:
 - For peroneal DL and tibial DL, using normal deviate.
 - For peroneal CMAP, peroneal CV and sural SNAP, using $(-1) \times$ normal deviate.
 - Vibration detection threshold (VDT): using normal deviate.
 - Heart rate response to deep breathing (HRdb): using $(-1) \times$ normal deviate.

Each normal deviate ranges from -3.72 to +3.72. The total score is calculated as the mean normal deviates of the non-missing 7 nerve tests multiplied by 7. The total score ranges from -26 to +26.

Missing values will be handled as follows:

- Missing items within the 7 nerve tests are handled in Step 4 above.
- If a component of NIS+7 (NIS-W, NIS-R, NIS-S, and 7 nerve tests) is missing from replicate A, then impute the component from replicate B → recover 2 complete replicate NIS+7 measures A and B.
- If both replicates A and B are incomplete at *different* components, insert A components into B and B components into A as necessary → recover 2 complete replicate NIS+7 measures A and B.
- If NIS-W component is missing from both replicates A & B, NIS+7 score is considered as missing. If 1 of the other NIS+7 components (NIS-R, NIS-S, and 7 nerve tests) is missing from both replicates A and B, impute this component as the average of the other patients at this time point who had non-missing data.
- If 1 entire NIS+7 replicate is missing, use the singular (other) replicate rather than the average of the 2 in subsequent calculations.
- If no single complete NIS+7 measure can be found or recovered, NIS+7 score is considered as missing.

In 006, if the last NIS+7 assessment in the parent study was done more than 45 days before the first dose in 006, NIS+7 will be reassessed on Day 1 in 006. It is expected that very few patients will have this Day 1 assessment; therefore, the imputation algorithm for missing components in NIS+7 will be slightly different from the general algorithm. If NIS-W is missing from both replicates, the NIS+7 total score will be considered as missing, similar to the general algorithm. If any other component is missing from both replicates, the component score will be imputed by LOCF using the imputed average component score from the last assessment in the parent study.

7.1.3. NIS Total Score

NIS total score is the sum of NIS-W, NIS-R, and NIS-S. The handling of missing data is similar as the steps described for mNIS+7. If NIS-W is missing from both replicates, NIS score is considered as missing.

7.1.4. Algorithms for Setting Normal Deviates and Points

For nerve conductions and HRdb tests, raw values are provided by the Mayo Clinic. Each raw value is first converted to a z-score which is then used to set either normal deviate or point score.

Z-scores are calculated using the following equations provided by the Mayo Clinic:

Parameter (abbreviation, units)	Z-score Equation
Heart Rate Response to Deep Breathing (HRdb, beats/min)	$HRdbz = HRdb - (28.87292939 + -0.24448047 * age)$
Ulnar CMAP (UMAE, mV)	$UMAEz = UMAE - (12.34105776660360 + -0.04413566229394 * age)$
Peroneal CMAP (PMAK, mV)	$PMAKz = PMAK - (7.26194271992764 + -0.04324792361150 * age)$
Peroneal MNCV (PMCVK, m/sec)	$PMCVKz = PMCVK - (87.98055432974630 + 0.01685327077581 * age + -0.00134262390616 * age^2 + -0.21761114034235 * height)$
Peroneal MNDL (PMLA, msec)	$PMLAz = PMLA - (4.97158112197395 + -0.36990514432031 * sex)$
Tibial CMAP (TMAK, mV)	$TMAKz = TMAK - (11.91330602787780 + 0.79541113237729 * age + -0.01622568048284 * age^2 + 0.00008722708244 * age^3 + -5.49838000227032 * bsa)$
Tibial MNDL (TMLA, msec)	$TMLAz = TMLA - (4.00321823725368 + 0.00588241012995 * age + -0.25248993385258 * sex)$
Sural SNAP (SSAB, uV)	$y = \ln(1+SSAB) - (5.58389110852732 + 0.01546531508256 * age + -0.01693664229181 * height + -0.00034198271691 * age^2)$ if $y > 0$ then $SSABz = y / (0.7001926549587 + -0.20662093194825 * bsa)$ else if $y \leq 0$ then $SSABz = y$
Wrist-Fifth Ulnar SNAP (USAW, uV)	$y = \ln(1+USAW) - (3.38461614473185 + -0.01702085210501 * age + 0.59463420483099 * sex)$ if $y > 0$ then $USAWz = y$ else if $y \leq 0$ then $USAWz = y / (0.16695910921534 + 0.00291051555416 * age)$
Notes: 1) sex is coded 1 = male, 2 = female 2) height is in cm 3) weight is in kg 4) $bsa = \text{body surface area (m}^2\text{)} = \text{weight}^{0.425} \times \text{height}^{0.725} \times 0.007184$ 5) age is an integer rounded down to the nearest year	

For a given parameter, the calculated z-score is then compared to 2 lookup tables (see below) using the following procedure to assign the normal deviate score:

1. If the calculated z-score value is less than the lower z-score value (ZLOWER) in the Extended Percentiles (EP) table, then the normal deviate value is the maximum of (-3.72, (z-score – ZLOWER + WLOWER)).
2. If the calculated z-score value is greater than or equal to ZLOWER and less than the minimum z-score value in the All Percentiles (AP) table, then the normal deviate value = -2.75.
3. If the calculated z-score value is greater than upper z-score value (ZUPPER) in the EP table, then the normal deviate value is the minimum of (3.72, (z-score – ZUPPER + WUPPER)).
4. If the calculated z-score value is less than or equal to ZUPPER and greater than the maximum z-score value in the AP table, then the normal deviate value = 2.75.

5. If the calculated z-score falls between 2 values in the AP table, select the z-score with the normal deviate value closer to 0 (i.e., the 50th percentile). The normal deviate value is the value from the Normal Deviate column corresponding to the selected z-score. For example, if PMLAZ = -0.8 then the PMLA normal deviate (PMLAND) value = -1.65. If PMLAZ = 2.2 then PMLAND = 2.37.
6. If the calculated z-score is less than or equal to the z-score corresponding to the 50th percentile and exactly matches a z-score for that parameter in the AP table, then select the row with the next highest z-score value. The normal deviate value is the value from the Normal Deviate column corresponding to the selected z-score. For example, if PMLAZ = -0.9017 then PMLAND = -1.88.
7. If the calculated z-score is greater than the z-score corresponding to the 50th percentile and exactly matches a z-score for that parameter in the AP table, then select the row with the next lowest z-score value. The normal deviate value is the value from the Normal Deviate column corresponding to the selected z-score. For example, if PMLAZ = 2.2682 then PMLAND = 2.37.

The points for the parameters are calculated as follows:

1. For PMLA, TMLA, and VDT: z-scores <1.65 are assigned 0 points, z-scores ≥ 1.65 but <2.33 are assigned 1 point, and z-scores ≥ 2.33 are assigned 2 points.
2. For HRdb, UMAE, PMAK, PMCVK, TMAK, SSAB, and USAW: z-scores > -1.65 are assigned 0 points, z-scores ≤ -1.65 but < -2.33 are assigned 1 point, and z-scores ≤ -2.33 are assigned 2 points.

All Percentiles Table

Percentile	Normal Deviate	HRdb	UMAE	PMAK	PMCVK	PMLA	TMAK	TMLA	USAW	SSAB
0.3	-2.75	-12.783	-5.5287	-4.6320	-9.3076	-1.0017	-7.6549	-0.9448	-4.5129	-2.3235
0.4	-2.65	-12.4944	-5.5287	-4.6320	-9.3076	-1.0017	-7.6549	-0.9448	-4.5129	-2.3235
0.5	-2.58	-12.4944	-5.5287	-4.6320	-9.3076	-1.0017	-7.6549	-0.9448	-4.5129	-2.3235
0.6	-2.51	-12.4944	-5.1192	-4.3753	-8.8001	-1.0017	-7.2749	-0.9037	-4.1808	-2.2050
0.7	-2.46	-12.2499	-5.1192	-4.3753	-8.8001	-1.0017	-7.2749	-0.9037	-4.1808	-2.2050
0.8	-2.41	-12.2499	-4.8488	-4.3712	-8.8001	-1.0017	-7.2270	-0.8394	-3.9289	-2.1063
0.9	-2.37	-12.2499	-4.8488	-4.3671	-8.7164	-0.9017	-7.2270	-0.8394	-3.9289	-2.1063
1	-2.33	-11.4044	-4.8488	-4.3671	-8.7164	-0.9017	-7.2270	-0.8394	-3.9289	-2.1063
2	-2.05	-10.6489	-4.0722	-3.8807	-6.9587	-0.9017	-7.0107	-0.7982	-2.7648	-1.0013
3	-1.88	-10.2499	-3.6577	-3.1211	-6.3385	-0.8017	-6.2660	-0.7159	-2.4600	-0.9160
4	-1.75	-10.0054	-3.4371	-3.0279	-5.5293	-0.8017	-5.7380	-0.6688	-2.0958	-0.7910
5	-1.65	-9.7388	-3.2846	-2.9915	-4.9611	-0.7318	-5.5688	-0.6335	-2.0534	-0.7595
6	-1.56	-9.3603	-3.1142	-2.9481	-4.7403	-0.7318	-5.0376	-0.5982	-1.9855	-0.7098
7	-1.48	-9.2041	-2.9929	-2.8510	-4.3695	-0.7017	-4.7452	-0.5625	-1.8139	-0.6757
8	-1.41	-8.3161	-2.9192	-2.7860	-4.3445	-0.6318	-4.4486	-0.5448	-1.7251	-0.6156
9	-1.34	-7.8272	-2.7729	-2.6320	-3.9685	-0.6318	-4.3632	-0.5037	-1.6250	-0.5995
10	-1.28	-7.2262	-2.6901	-2.4320	-3.7034	-0.6017	-4.2040	-0.4865	-1.6014	-0.5764
11	-1.23	-7.0496	-2.5750	-2.3156	-3.4907	-0.6017	-4.0853	-0.4743	-1.4781	-0.5648
12	-1.18	-6.9596	-2.4377	-2.2738	-3.2399	-0.6017	-3.9092	-0.4512	-1.4231	-0.5289
13	-1.13	-6.783	-2.3142	-2.1563	-2.9994	-0.5318	-3.8051	-0.4394	-1.3393	-0.5133
14	-1.08	-6.6489	-2.1605	-2.0428	-2.9135	-0.5318	-3.6773	-0.4277	-1.2372	-0.4995
15	-1.04	-6.3603	-2.0225	-1.9645	-2.8256	-0.5318	-3.5900	-0.4100	-1.1589	-0.4773
16	-0.99	-6.2041	-1.9701	-1.8968	-2.7349	-0.5318	-3.4409	-0.4037	-1.1203	-0.4555
17	-0.95	-5.9833	-1.9080	-1.8590	-2.6739	-0.5318	-3.2858	-0.3865	-1.0880	-0.4279
18	-0.92	-5.9596	-1.8577	-1.8346	-2.4869	-0.5017	-3.1555	-0.3860	-1.0282	-0.4215
19	-0.88	-5.8713	-1.7605	-1.7293	-2.3484	-0.5017	-3.0824	-0.3684	-0.9673	-0.3858
20	-0.84	-5.7593	-1.7019	-1.6495	-2.2547	-0.5017	-2.9948	-0.3512	-0.9323	-0.3752
21	-0.81	-5.5827	-1.6695	-1.6238	-2.1736	-0.4318	-2.8392	-0.3448	-0.9115	-0.3611
22	-0.77	-5.4707	-1.6377	-1.5266	-2.1275	-0.4318	-2.6699	-0.3394	-0.8764	-0.3578
23	-0.74	-5.3382	-1.5426	-1.4375	-2.0479	-0.4017	-2.6461	-0.3218	-0.8461	-0.3288
24	-0.71	-5.2703	-1.4818	-1.3954	-1.9541	-0.4017	-2.5639	-0.3213	-0.8201	-0.3198
25	-0.67	-4.9817	-1.3633	-1.3401	-1.8102	-0.3318	-2.4213	-0.3159	-0.8141	-0.3080
26	-0.64	-4.9596	-1.3102	-1.2428	-1.6411	-0.3318	-2.3032	-0.3037	-0.7693	-0.2923
27	-0.61	-4.6268	-1.2259	-1.1266	-1.5417	-0.3318	-2.2417	-0.2978	-0.7567	-0.2861
28	-0.58	-4.4486	-1.1722	-1.0847	-1.4258	-0.3318	-2.1872	-0.2688	-0.7011	-0.2745
29	-0.55	-4.2041	-1.0840	-1.0103	-1.3566	-0.3017	-2.0659	-0.2453	-0.6843	-0.2657
30	-0.52	-4.0937	-1.0488	-1.0021	-1.2907	-0.3017	-2.0309	-0.2335	-0.6642	-0.2466
31	-0.5	-4.0038	-1.0142	-0.9508	-1.2377	-0.3017	-1.9931	-0.2277	-0.6416	-0.2374
32	-0.47	-3.7814	-0.9253	-0.9198	-1.0846	-0.3017	-1.9077	-0.2218	-0.5357	-0.2242
33	-0.44	-3.6268	-0.8750	-0.8671	-0.9904	-0.2318	-1.7583	-0.2159	-0.5096	-0.1981
34	-0.41	-3.4707	-0.7778	-0.8158	-0.9556	-0.2318	-1.6953	-0.2096	-0.4527	-0.1894

35	-0.39	-3.2924	-0.7371	-0.7618	-0.8822	-0.2318	-1.6426	-0.1924	-0.3916	-0.1858
36	-0.36	-3.182	-0.7074	-0.7523	-0.8417	-0.2318	-1.6022	-0.1860	-0.3633	-0.1721
37	-0.33	-3.0479	-0.6701	-0.6942	-0.7822	-0.2318	-1.5846	-0.1747	-0.3306	-0.1566
38	-0.31	-3.0259	-0.6287	-0.6483	-0.6634	-0.2017	-1.5418	-0.1688	-0.2903	-0.1415
39	-0.28	-2.9596	-0.5661	-0.6078	-0.6256	-0.2017	-1.3820	-0.1566	-0.2631	-0.1236
40	-0.25	-2.8272	-0.4846	-0.5467	-0.5417	-0.2017	-1.3434	-0.1507	-0.2465	-0.1043
41	-0.23	-2.7388	-0.4074	-0.5348	-0.4421	-0.1318	-1.2323	-0.1390	-0.2363	-0.0878
42	-0.2	-2.671	-0.3633	-0.4346	-0.3655	-0.1318	-1.2023	-0.1277	-0.2028	-0.0774
43	-0.18	-2.2041	-0.2985	-0.3995	-0.3276	-0.1318	-1.0807	-0.1213	-0.1897	-0.0668
44	-0.15	-2.1599	-0.2516	-0.3077	-0.2133	-0.1318	-0.8723	-0.1154	-0.1189	-0.0559
45	-0.13	-2.0038	-0.1454	-0.2103	-0.1076	-0.1017	-0.8126	-0.1096	-0.0814	-0.0369
46	-0.1	-1.8713	-0.1019	-0.1778	-0.0405	-0.1017	-0.7094	-0.0924	-0.0478	-0.0225
47	-0.08	-1.6489	-0.0343	-0.1373	-0.0001	-0.1017	-0.5876	-0.0801	-0.0218	-0.0129
48	-0.05	-1.6047	-0.0170	-0.1143	0.0387	-0.1017	-0.5527	-0.0743	0.0061	-0.0013
49	-0.03	-1.3382	0.0160	-0.1048	0.0957	-0.0318	-0.4625	-0.0629	0.0136	0.0217
50	0	-1.0937	0.0623	-0.0618	0.1549	-0.0318	-0.3295	-0.0512	0.0188	0.0689
51	0.03	-1.0275	0.0830	0.0032	0.2071	-0.0318	-0.2915	-0.0448	0.0190	0.1077
52	0.05	-0.7814	0.1278	0.0654	0.2973	-0.0017	-0.1557	-0.0390	0.0248	0.1716
53	0.08	-0.7593	0.1602	0.1059	0.3555	-0.0017	-0.1220	-0.0331	0.0348	0.1897
54	0.1	-0.4944	0.1802	0.1572	0.3712	-0.0017	-0.0486	-0.0213	0.0413	0.2291
55	0.13	-0.0937	0.2484	0.2032	0.4167	-0.0017	0.1142	-0.0096	0.0479	0.2536
56	0.15	0.217	0.2947	0.2220	0.4744	0.0682	0.2349	-0.0041	0.0566	0.2940
57	0.18	0.4173	0.3299	0.2490	0.5896	0.0682	0.3547	0.0253	0.0679	0.3011
58	0.2	0.5735	0.4133	0.3410	0.6710	0.0682	0.4620	0.0316	0.0888	0.3257
59	0.23	0.6618	0.4568	0.4220	0.7195	0.0682	0.5717	0.0547	0.0932	0.3661
60	0.25	0.8842	0.5222	0.4734	0.7472	0.0682	0.6988	0.0665	0.1035	0.3965
61	0.28	1.0404	0.5747	0.4950	0.7809	0.0682	0.8750	0.0669	0.1171	0.4216
62	0.31	1.1949	0.6574	0.5681	0.8423	0.0682	0.9640	0.0782	0.1228	0.4373
63	0.33	1.2612	0.7423	0.6625	0.9056	0.0983	1.1068	0.0841	0.1330	0.4770
64	0.36	1.5293	0.7830	0.6869	0.9563	0.0983	1.1252	0.0963	0.1398	0.4957
65	0.39	1.706	0.8250	0.7114	1.0163	0.0983	1.2375	0.1140	0.1501	0.5152
66	0.41	1.8621	0.8540	0.7681	1.0514	0.0983	1.2980	0.1199	0.1575	0.5415
67	0.44	1.9962	0.8892	0.8490	1.1319	0.1682	1.5574	0.1316	0.1721	0.5839
68	0.47	2.1287	0.9389	0.9058	1.2285	0.1682	1.6796	0.1493	0.1822	0.6237
69	0.5	2.2612	1.0037	0.9463	1.3007	0.1682	1.8460	0.1669	0.1872	0.6942
70	0.52	2.7738	1.0629	0.9627	1.4587	0.1983	1.8750	0.1782	0.1953	0.7186
71	0.55	3.3511	1.1305	1.0895	1.5916	0.1983	1.9733	0.1841	0.2049	0.7646
72	0.58	3.706	1.1484	1.1613	1.6512	0.2682	2.0584	0.1904	0.2115	0.8278
73	0.61	4.0167	1.2271	1.1922	1.7069	0.2682	2.1753	0.2194	0.2320	0.8722
74	0.64	4.2407	1.2808	1.2355	1.7460	0.2682	2.2577	0.2257	0.2492	0.9115
75	0.67	4.4836	1.3802	1.2762	1.7924	0.2983	2.3567	0.2434	0.2622	0.9370
76	0.71	4.6839	1.4719	1.3398	1.8449	0.2983	2.6142	0.2665	0.2779	0.9709
77	0.74	5.1508	1.5133	1.3922	1.9352	0.2983	2.7013	0.2846	0.2955	0.9916
78	0.77	5.5514	1.5747	1.4815	2.2061	0.3682	2.7523	0.3081	0.3004	1.0341
79	0.81	5.7297	1.6099	1.5627	2.3972	0.3682	2.8504	0.3199	0.3205	1.0512

80	0.84	6.1066	1.7065	1.6491	2.5217	0.3682	3.0249	0.3312	0.3330	1.0760
81	0.88	6.4173	1.7802	1.7247	2.5986	0.3983	3.1374	0.3434	0.3382	1.1249
82	0.92	6.5293	1.8802	1.8599	2.7346	0.3983	3.2372	0.3547	0.3524	1.1720
83	0.95	6.7076	1.9395	1.9140	2.8123	0.4682	3.3970	0.3846	0.3572	1.2310
84	0.99	7.2391	2.0244	1.9801	2.9923	0.4983	3.5065	0.4199	0.3732	1.2883
85	1.04	7.6177	2.1450	1.9924	3.0338	0.4983	3.6598	0.4547	0.3822	1.3203
86	1.08	8.0845	2.2395	2.0627	3.1704	0.5682	3.8320	0.4782	0.3962	1.3679
87	1.13	8.217	2.3305	2.1275	3.2896	0.5983	3.8959	0.4959	0.4054	1.3814
88	1.18	8.5514	2.5574	2.1924	3.4144	0.5983	4.2745	0.5900	0.4366	1.5034
89	1.23	9.0404	2.6361	2.2815	3.5946	0.6682	4.4199	0.6076	0.4498	1.5338
90	1.28	9.1949	2.7657	2.3654	3.7666	0.6983	4.4980	0.6257	0.4756	1.6781
91	1.34	9.5073	2.9512	2.4599	3.8362	0.7682	4.7815	0.6488	0.4876	1.7277
92	1.41	9.7297	3.0596	2.5342	3.9685	0.8682	4.9848	0.6552	0.4995	1.7787
93	1.48	9.9741	3.2333	2.7005	4.1271	0.9682	5.3345	0.6787	0.5271	1.8612
94	1.56	10.9521	3.4389	2.7815	4.3815	0.9983	5.5661	0.7665	0.5548	1.9634
95	1.65	11.728	3.6568	2.9652	4.6629	1.0682	6.1351	0.7963	0.5886	2.0163
96	1.75	12.4836	3.7333	3.1627	5.0363	1.1682	6.3302	0.8199	0.6115	2.1509
97	1.88	13.8401	3.9250	3.8382	5.1400	1.2983	6.9363	0.9140	0.6422	2.2184
98	2.05	14.6618	4.3540	4.0519	5.5861	1.5983	7.9601	1.1959	0.7477	2.4046
99	2.33	17.728	5.1216	4.3517	7.3224	1.8983	9.8583	1.3963	0.8782	2.8233
99.1	2.37	20.0845	5.1216	4.3517	7.3224	1.8983	9.8583	1.3963	0.8782	2.8233
99.2	2.41	20.0845	5.1216	4.4761	7.4064	2.2682	9.8583	1.3963	0.8782	2.8233
99.3	2.46	20.0845	5.1685	4.6005	7.4064	2.2682	10.0358	1.4371	0.8803	2.9923
99.4	2.51	21.1728	5.1685	4.6005	7.4064	2.2682	10.0358	1.4371	0.8803	2.9923
99.5	2.58	21.1728	7.4830	6.2977	7.6495	2.5983	10.3303	1.6728	0.8973	3.0371
99.6	2.65	21.1728	7.4830	6.2977	7.6495	2.5983	10.3303	1.6728	0.8973	3.0371
99.7	2.75	25.7517	7.4830	6.2977	7.6495	2.5983	10.3303	1.6728	0.8973	3.0371

Extended Percentiles Table

Variable	WLOWER	WUPPER	ZLOWER	ZUPPER
HRdb	-2.65	2.65	-12.6387	23.4623
UMAE	-2.75	2.75	-7.4715	7.5668
PMAK	-2.75	2.75	-5.1036	6.4342
PMCVK	-2.75	2.75	-9.3393	8.1941
PMLA	-2.75	2.75	-1.0517	3.0833
TMAK	-2.75	2.75	-7.7785	10.6018
TMLA	-2.75	2.75	-0.9831	3.414
USAW	-2.75	2.75	-6.5249	0.9233
SSAB	-2.75	2.75	-2.3692	3.2713

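### SAP Section 7.1.4 applies the 5th/1st-percentile normal-deviate cut-offs (-1.65/-2.33) to 'z-scores' that are residuals, so the point thresholds for all five Σ5 nerves miss the percentile bands that define the mNIS+7 score

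*SAP*

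**What the plan says.** **What defines the points.** SAP Section 7.1.1.1, item 4, bases the Σ5 points on percentiles in a healthy reference cohort: "these percentile values were expressed as points from obtained percentile values". Above the 5th percentile scores 0, at or below the 5th but above the 1st scores 1, and at or below the 1st scores 2. Σ5 is five times the mean over the non-missing tests, with a maximum of 10.

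**What the points are computed from.** Section 7.1.4 states: "Each raw value is first converted to a z-score which is then used to set either normal deviate or point score". Normal deviate and point score are thus two alternative outputs of the z-score. The z-score equations for ulnar and peroneal CMAP are "UMAEz = UMAE - (12.34105776660360 + -0.04413566229394 * age") and "PMAKz = PMAK - (7.26194271992764 + -0.04324792361150 * age"), i.e. observed minus predicted in mV. Tibial CMAP has the same form with more predictors. Sural SNAP is a log-scale residual, left unscaled when it is zero or negative. Ulnar SNAP is a log-scale residual, divided by an age-dependent term when it is zero or negative.

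**The point rule.** For the tests in which low values are abnormal: "For HRdb, UMAE, PMAK, PMCVK, TMAK, SSAB, and USAW: z-scores > -1.65 are assigned 0 points", followed by "z-scores ≤ -1.65 but < -2.33 are assigned 1 point, and z-scores ≤ -2.33 are assigned 2 points".

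**The lookup table.** The All Percentiles table lists, for each percentile, a normal deviate and the z-score of each test. Its 5th-percentile row has normal deviate -1.65 and its 1st-percentile row has -2.33.

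**The concern.** The numbers -1.65 and -2.33 belong to the normal-deviate column of the lookup table, but the rule compares them with the z-score, which is on a different scale for each test. A programmer who follows Section 7.1.4 and one who follows Section 7.1.1.1 would give different points to the same measurement.

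Σ5 is a component of mNIS+7, and Section 4.5 summarises observed values and changes from baseline for both components and composite. The misplacement differs in direction between nerves, so it is not a constant shift. CMAP points reach their ceiling of 2 too early, while sural loss registers too late. Both move the points at which change over time becomes visible.

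**Working it through.** **1. The SAP's own figures.** Standard normal quantiles are z(0.05) = -1.645 and z(0.01) = -2.326, which round to the table's -1.65 and -2.33. The cut-offs are therefore normal deviates of the 5th and 1st percentiles.

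**2. Where the cut-offs fall on the z-score scale.** Inputs are the All Percentiles columns for the five Σ5 tests. I interpolated linearly between adjacent rows. For ulnar CMAP, -1.65 lies between -1.6695 (21st) and -1.6377 (22nd): 21 + (1.6695 - 1.65)/(1.6695 - 1.6377) = 21.6.

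| Test | z-score at 5th / 1st percentile | Percentile at which -1.65 / -2.33 falls | Target |
|---|---|---|---|
| Ulnar CMAP (UMAE) | -3.28 / -4.85 | 21.6 / 12.9 | 5 / 1 |
| Peroneal CMAP (PMAK) | -2.99 / -4.37 | 20.0 / 10.9 | 5 / 1 |
| Tibial CMAP (TMAK) | -5.57 / -7.23 | 34.9 / 25.8 | 5 / 1 |
| Ulnar SNAP (USAW) | -2.05 / -3.93 | 8.8 / 3.4 | 5 / 1 |
| Sural SNAP (SSAB) | -0.76 / -2.11 | 1.4 / below 0.3 | 5 / 1 |

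The first four are reached too easily (over-scoring); the sural cut-offs are too hard to reach (under-scoring).

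**3. Expected Σ5 in the reference population.** Read literally, the 1-point band (at or below -1.65 but also below -2.33) overlaps the 2-point band and leaves most of the interval between the two cut-offs unscored. I repaired it to above -2.33. Each test's expected points are then P(z ≤ -1.65) + P(z ≤ -2.33).

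- UMAE 0.345, PMAK 0.309, TMAK 0.606, USAW 0.121, SSAB 0.017 (taking 0.3% for the value off the table).
- Sum: 1.398, about 1.40.
- Percentile rule: 5 × (0.05 + 0.01) = 0.30.
- Difference: about 1.10 of 10 Σ5 points, or 1.10/304 = 0.4% of the mNIS+7 range.

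**4. Single measurements** (inequality repaired).

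- Ulnar CMAP at age 60: predicted 12.341 - 0.04414 × 60 = 9.69 mV.
  - 8.0 mV gives -1.69, about the 20th percentile: 1 point as written, 0 by percentile.
  - 7.0 mV gives -2.69, about the 10th percentile: 2 points as written, 0 by percentile.
  - An absent response gives -9.69: 2 points either way.
- Absent sural response, age 65, 170 cm: -(5.5839 + 1.0052 - 2.8792 - 1.4449) = -2.265, below the 1st-percentile value of -2.1063: 1 point as written, 2 by percentile.
- Absent sural response, age 80, 180 cm: -(5.5839 + 1.2372 - 3.0486 - 2.1887) = -1.584, between the 1st and 2nd percentiles: 0 points as written, 1 by percentile.

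**5. Does the normal deviate repair it?** Under the lookup rules, a ulnar CMAP residual between the 4th- and 5th-percentile values takes the 5th-percentile deviate, -1.65, and scores 1; one between the 5th and 6th takes -1.56 and scores 0. This agrees with Section 7.1.1.1. The exception is an exact match: lookup rule 6 moves -3.2846 to -1.56 (0 points, where the percentile rule gives 1) and -4.8488 to -2.05 (1 point, where it gives 2).

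**The case against.** The strongest reply is that 'z-scores' in the point rule is a slip for normal deviates. Section 7.1.1.1 gives the percentile definition correctly, the cut-offs match the normal-deviate column exactly, and the same sentence contains an obvious inequality slip. The program may well be right. What stands is that nothing in the SAP shows data to have been mis-scored. The slip reading does not rescue the text, however. Section 7.1.4 names the z-score as the input for points and keeps the two terms apart in every lookup rule.

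Other limits also stand:

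- The ulnar SNAP z-score is scaled in the tail that is scored, so it is not a raw residual. Its cut-offs still miss the 5th and 1st percentiles.
- A reader might infer that every patient's Σ5 is wrong. The cut-offs are wrong for every nerve, but a value beyond both sets of cut-offs gets the same points, as the absent ulnar CMAP shows.
- NIS+7 uses normal deviates (Section 7.1.2) and NIS has no conduction component (Section 7.1.3), so neither is touched. Points for the distal latencies, VDT, HRdb and peroneal velocity enter no score in this SAP.
- The study is descriptive, without hypothesis tests (Section 3.2).

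**Conclusion.** The point rule in Section 7.1.4 is wrong as written and contradicts Section 7.1.1.1 and the lookup table. For all five Σ5 nerves the cut-offs miss the intended percentiles, giving over-scoring for the three CMAPs and the ulnar SNAP and under-scoring for the sural SNAP. In the healthy reference, expected Σ5 is about 1.40 against 0.30. This assumes linear interpolation in the table, all five tests present and the reversed inequality repaired.

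A reader might carry the 1.10-point excess over to the trial's patients or to their change from baseline. The documents do not support that: the figure describes a healthy population, many patients may lie beyond both sets of cut-offs, and the sural error runs the other way. The effect is confined to a component worth at most 10 of 304 mNIS+7 points. It still needs correcting, because the SAP gives two different scores for one measurement.

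**What to change.** 1. State the lower-tail point rule, which covers all five Σ5 nerves, on the normal deviate from the lookup procedure, or on the percentile: above -1.65 = 0; at or below -1.65 and above -2.33 = 1; at or below -2.33 = 2. This also corrects the reversed inequality. Mirror it for PMLA and TMLA.
2. State that a residual exactly equal to the 5th- or 1st-percentile table value is scored by the at-or-below rule of Section 7.1.1.1, because lookup rule 6 would move it one row toward the median.
3. For VDT, refer to the externally derived normal deviate, since Section 7.1.4 has no VDT equation or lookup column.
4. Change the sentence that makes the z-score the direct input for points.
5. Check the program against the corrected rule and re-derive Σ5 and mNIS+7 if it followed the current text.
6. Confirm that parent-study assessments serving as baseline (Section 3.4) and Study 006 visits are scored by the same rule. If they differ, change from baseline would include an artefact. The parent algorithm is not shown, so this is a check, not a finding.

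The cost is SAP wording and a programming check, plus rescoring of stored values if a discrepancy is found, in the parent study as well where its scores serve as baseline. No new data are needed.
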